### Sample size

The sample size is 965 patients.

### Procedure

Patients who agree to participate and sign the informed consent will undergo a neuropsychological assessment (after 5 years of follow-up) with the same test battery as in the first evaluation (performed between 2014-2017) by trained interviewers and The clinical variables (morbidity and cardiovascular risk factors) and treatment variables will be collected through a clinical interview.

Anthropometric variables, as well as chronic diseases and medication will be collected by the patient's doctor. The rest of the information will be collected by interviewers. See Table 1.

Table 1. Variables and measurements collected during the study

	Variables collected at baseline	Variables collected after 5 years of follow-up
Social and demographic variables collected by interviewers: - Age - Gender - Marital status - Education - Profession	X X X X X	X X
Health related variables collected by primary care physicians: - Blood pressure - Cholesterol levels - Weight and height - Morbidity - Pharmacotherapeutic treatment	X X X X X	X X X X X
Variables on lifestyle and health status collected by interviewers: - Alcohol consumption - Caffeine consumption - Tobacco use - Physical activity - Mediterranean diet - EuroQoL 5D-3L - Quality of life measurement scales	X X X X X X	X X X X X X
Neuropsychological assessment carried out by interviewers: - CES-D scale - Word accentuation test - MMSE 37 - Instrumental activities of daily living, Pfeffer scale	X X X	X X X

 
- Semantic Verbal Fluency test
 
- Six-Object Memory Recall Test
 
- Trail Making test
 
- Clock-drawing test
 
	X	X
Exposure variables calculated by the research team:		

 
- Framingham REGICOR function
 
- FRESCO function
 
	X	X
	X	X

CES-D scale: Center for Epidemiologic Studies Depression Scale; MMSE-37: Mini Mental State Examination 37 item-version; FRESCO: Función de Riesgo Española de acontecimientos Coronarios y Otros; REGICOR: Registre Gironí del Cor

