## **OBJECTIVES**

### **Primary**

The main objective is to evaluate the association between cardiovascular risk, calculated with the Framingham REGICOR and FRESCO risk functions, and the cognitive decline after 5 years of follow-up in the NEDICES-2-RISK cohort.

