## **METHODS / DESIGN**

**Design.** Prospective longitudinal analytical observational study of cohort with 5 years of follow-up.

**Scope of study.** The scope of study is the Primary Care setting of the Spanish national health system.

**Study population.** The population of the NEDICES-2-RISK study are patients aged 55 to 74 who were included in the NEDICES-2 cohort (2014-2017), in which the presence of dementia in the initial neuropsychological evaluation was ruled out. The population of the NEDICES-2 study comes from the list of users with health cards of the participating doctors of the health centers

included and the sample selection was carried out by random sampling stratified by sex and age in groups of 5-year increase of people of 55 years and over.

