### Patient selection criteria.

1. Inclusion criteria:
  - a. Age 55 to 74 years
  - b. Agreeing to participate and provide written informed consent
  - c. Having completed the neuropsychological assessment of the NEDICES-2 study
2. Exclusion criteria:
  - a. To have dementia at the beginning of the study

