## STATISTICAL ANALYSIS

Initially, a review of the quality of the study data will be carried out: detection of errors in the coding, missing data and possible biases related to representativeness of the sample (for example, selection of subjects and loss in follow-up, among others).

Different descriptive statistics will be used to analyze the baseline characteristics (qualitative and quantitative variables) of the patients included in the study. For the categorical variables, such as the sociodemographic and clinical variables of the patients, they will be analyzed and represented by frequency tables (globally and by strata). For numerical variables, means and standard deviations will be calculated. Patients who leave the study will be described, including the characteristics of the patients and the reasons for the loss of follow-up.

The bivariate analysis will try to find the presence of a significant association between baseline cardiovascular risk and the score obtained in the cognitive and functional tests (MMSE 37, Trail Making Test, Semantic Verbal Fluency test, Six-Object Memory Recall Test, Clock drawing test, Pfeffer functional assessment scale). For this, the Pearson's Chi-square and Spearman statistical coefficients will be used, as appropriate.

Finally, multivariate analyses (multiple regression, analysis of covariance) will study the association between baseline cardiovascular risk (4 categories) and the psychometric and functional tests adjusted for relevant sociodemographic and clinical variables as potential confounding factors. Linear regression models of mixed effects (which take into account intrasubject variability when considering repeated measures) will be used, considering as a dependent variable the score obtained in each of the tests studied (one model for each scale) and as an independent, the cardiovascular risk basal (4 categories).

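### People who become demented or too impaired to sign or be tested have no place in the 5-year outcome, which may pull the primary association toward zero

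*Combined protocol and SAP*

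**What the plan says.** The primary objective relates baseline REGICOR and FRESCO risk to "and the cognitive decline after 5 years of follow-up in the NEDICES-2-RISK cohort".

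- **Entry.** Inclusion criterion (b) is "Agreeing to participate and provide written informed consent". Criterion (c) requires a completed NEDICES-2 battery. The Procedure section links signing to the later test: "Patients who agree to participate and sign the informed consent will undergo a neuropsychological assessment (after 5 years of follow-up".
- **Dementia.** It appears only as a starting condition. The exclusion criterion is "To have dementia at the beginning of the study", and the study-population paragraph describes a cohort "in which the presence of dementia in the initial neuropsychological evaluation was ruled out".
- **Outcomes.** The multivariate analyses "will study the association between baseline cardiovascular risk (4 categories) and the psychometric and functional tests". The mixed models are specified as "considering as a dependent variable the score obtained in each of the tests studied", one per scale. The last paragraph of the Statistical Analysis section adds reliable change in each test. There is no 5-year dementia outcome and no scoring rule for someone who cannot be tested.
- **Losses.** The Statistical Analysis section opens with a data-quality review that covers selection and attrition bias, and it plans to describe leavers and their reasons. It names no analysis that adjusts for either.
- **Other data.** Table 1 has the primary care physician recording morbidity at baseline and again at 5 years. Dementia is not named there.

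**The concern.** The chance of having a 5-year score may depend on what that score would have been. Someone who has lost capacity since 2014-2017 may not sign, and someone who signs may not be able to complete the battery. In either case the largest declines are the ones most likely to be missing.

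The study's premise is that cardiovascular risk increases cognitive deterioration. If so, these missing people are concentrated in the highest risk category, and the comparison across categories understates the association that the primary objective asks about. The opening section justifies the study by dementia prevention, so the participants at issue are the ones of most interest.

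**Working it through.** **1. Plan's own figures.** The only design figure is the sample size of 965. No effect size, SD, power, attrition or incidence is given, so 965 cannot be reproduced, and the plan does not say whether it counts people eligible at baseline or people reassessed. The point does not depend on how 965 was derived. All inputs below other than 965, the four risk categories and the 0.05 level are assumptions.

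**2. Number of people.** At an assumed 5-year dementia incidence of 2-5%: 965 × 0.02 = 19 and 965 × 0.05 = 48.

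**3. Loss on the MMSE-37 scale.** Approximately,

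lost contrast (top minus bottom category) = incidence gap × extra drop with dementia × share of cases not assessed.

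| Case | Gap | Extra drop | Share missed | Lost contrast |
|---|---|---|---|---|
| Low | 0.02 | 6 | 0.50 | 0.06 |
| Midpoints | 0.04 | 8 | 0.75 | 0.24 |
| High | 0.06 | 10 | 1.00 | 0.60 |

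For scale, suppose the difference among people without dementia were 0.5 points. At the midpoints the full contrast would be 0.5 + 0.04 × 8 = 0.82, and the study would see about 0.82 − 0.24 = 0.58.

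**4. Same question in SD units.** With everyone seen, the contrast is d0 + (pH − pL) × D. Here d0 is the difference without dementia, pL and pH are the incidences in the low and high categories, and D is the extra decline with dementia. If a share m of cases is unseen, each p becomes p(1 − m)/(1 − pm).

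| d0 | pL | pH | D | All seen | Half unseen | All unseen |
|---|---|---|---|---|---|---|
| 0.20 | 1% | 2% | 1.5 | 0.215 | 0.208 (97%) | 0.200 (93%) |
| 0.20 | 2% | 6% | 2.5 | 0.300 | 0.252 (84%) | 0.200 (67%) |
| 0.10 | 3% | 10% | 2.5 | 0.275 | 0.194 (71%) | 0.100 (36%) |

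The first and last rows are the extremes of the grid examined (d0 0.10-0.20, pL 1-3%, pH 2-10%, D 1.5-2.5).

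**5. Power in the second row.** Four equal categories give 965/4 ≈ 241 each; a two-sided 0.05 test is assumed. With everyone seen, the SD is √(1 + ½(0.02 × 0.98 + 0.06 × 0.94) × 2.5²) = 1.11, and power for 0.300 is 84%. With all cases absent, about 241 × 0.96 = 231 remain per category, and power for 0.200 at SD 1 is 58%.

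**6. A gentler mechanism.** If retention falls smoothly with decline (70-80% retained overall, odds of being seen changing 1.35- to 2.7-fold per SD), simulation keeps 84-98% of the contrast.

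The direction is toward zero in every scenario with outcome-dependent loss. The size runs from minor to large.

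**The case against.** Several counter-arguments have force.

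- **Consent.** A reader might infer that only the participant's own signature counts and that it is taken just before the 5-year visit. The text says neither. Consent pages are not part of the supplied document, so a representative's route cannot be ruled out, and the Procedure section gives no signing date. This weakens the consent part of the argument. It does not supply an outcome for someone who cannot be tested.
- **Exclusion criterion.** A reader might infer that it removes people demented by the time of the 5-year visit. The study-population paragraph puts the dementia check at the initial evaluation, and Table 1 treats baseline as part of the study. Nothing excludes a person with incident dementia who can still be tested.
- **Bias review.** The plan does name selection and attrition as possible biases, and people not reassessed could be counted as lost because the population is defined by NEDICES-2 membership. That is a fair acknowledgement, but it is descriptive only.
- **Mixed models.** They use baseline scores from incomplete cases, validly if data are missing at random. Loss driven by the unseen 5-year state breaks that condition, and a person never enrolled may not be in the dataset at all.
- **Choice of endpoint.** The objective is cognitive decline, and the Pfeffer scale and reliable-change cutoffs are already planned. Lack of a dementia endpoint is not an error in itself. The gap is that these measures also need a testable participant.

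**Conclusion.** The concern holds as a possible bias toward zero in the primary association. It rests on three conditions: dementia incidence rises with baseline risk, dementia brings a large extra drop, and an appreciable share of those people are not assessed. The documents quantify none of these. On the assumptions shown, the loss is 0.06-0.60 MMSE-37 points, with 0.24 at the midpoints. In SD terms, 36-93% of the contrast is kept if every case is unseen and 71-97% if half are.

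A reader might go further and infer that a null result would be uninterpretable. The documents do not support that: some participants with incident dementia may well be tested, and at the mild end the attenuation is trivial. The supportable conclusion is that the plan as written has no analysis that would show which situation applies, so a weak or null finding would be hard to interpret without one.

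**What to change.** 1. Define the analysis cohort as all NEDICES-2 participants aged 55-74 and dementia-free at the 2014-2017 evaluation. Dating the exclusion criterion to that evaluation is a wording clarification that agrees with the study-population paragraph.
2. Report, by baseline risk category, how many were reassessed, refused, were unable, or died.
3. Prespecify a companion analysis of the primary objective, beside the score models, in which incident dementia or untestability for cognitive reasons counts as decline. It could be a binary outcome (reliable decline or incident dementia) or a worst-rank analysis. For enrolled participants, the physician morbidity record at 5 years can be the source if dementia is recorded explicitly.
4. Add a sensitivity analysis for people not reassessed, for example delta-adjusted scores.
5. Use records or a representative's consent for people who do not sign only where ethics approval allows. Items 1-4 can go ahead without it, but without such data the dementia status of non-signers stays unknown and item 4 has to carry that uncertainty.

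**Cost.** Short wording changes, a follow-up table, one companion analysis and one sensitivity analysis. The morbidity record is planned only for enrolled patients, so reaching non-signers would be extra work. Physician-recorded dementia is less uniform than a test score, so this analysis should supplement the score models and not replace them.

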**Cardiovascular Risk in People Older Than 55 Years and  
Cognitive Performance at 5 Years: an Estimation Model Based  
on Spanish Population. NEDICES-2-RISK study.**

NCT 03925844

Document Date: July 6, 2019

Dementia is unique in terms of prevalence, cost and impact. Any small advance in the prevention of dementia would benefit millions of people. Current data indicate that cardiovascular risk factors increase the risk of cognitive decline. The cardiovascular risk estimation by means of cardiovascular risk functions seems to be useful in the prediction of risk of cognitive deterioration. However, in the Spanish population, the incidence of coronary heart disease and stroke are lower than expected taking into account the cardiovascular risk factors.

The purpose of this study is to study the association between the cardiovascular risk of the study population, using the Framingham REGICOR and FRESCO cardiovascular risk functions, and the cognitive performance after 5 years of follow-up. The identification of individuals who have a high risk of cognitive decline in later years using predictive models of vascular risk would be a good approach to the prevention of cognitive impairment.

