In addition, the reliable change in each of the tests will be analyzed to verify which clinically significant changes occur in subjects with high cardiovascular risk. The reliable change will be analyzed following the Hsu method, while the McSweeny and Duff method will be used to calculate simple and complex standards based in regression to estimate the cutoff points of change adjusted for age, sex and educational level. The data analysis will try to adhere to the standards for the diagnostic accuracy report. A statistically significant association will be considered when the contrast statistic has  $p < 0.05$ .

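### The stated analysis names no elapsed time between baseline and retest, although baselines span 2014-2017 and no retest window is set, so actual intervals may vary.

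*Combined protocol and SAP*

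**What the plan says.** METHODS / DESIGN describes a "Prospective longitudinal analytical observational study of cohort with 5 years of follow-up" in patients "who were included in the NEDICES-2 cohort (2014-2017". The primary objective concerns "the cognitive decline after 5 years of follow-up in the NEDICES-2-RISK cohort". Under Procedure, consenting patients "will undergo a neuropsychological assessment (after 5 years of follow-up", "with the same test battery as in the first evaluation (performed between 2014-2017". No visit window, calling order or rule for early or late retests is given. The title page carries "Document Date: July 6, 2019", and the retest is written in the future tense.

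Under STATISTICAL ANALYSIS, the mixed models take the score on each scale as dependent variable and, "as an independent, the cardiovascular risk basal (4 categories". The preceding sentence promises adjustment for sociodemographic and clinical confounders without listing them. Reliable change is analysed as well, with regression-based standards used "to estimate the cutoff points of change adjusted for age, sex and educational level". Neither place names the time between the two tests or a term for risk by time.

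**The concern.** Elapsed time is part of the outcome, because the objective is decline over five years. Baseline dates spread over up to four calendar years, combined with a retest timed only nominally, leave room for real intervals to differ between patients. Cognitive change accrues with time, so a patient seen later has had longer to decline. A cut-off that ignores the interval treats that patient like one seen at exactly 5 years.

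Two things are at stake. Individual reliable-change classifications become noisier, and late-seen patients move towards the cut-off whatever their risk. If the interval also differed by risk category, the extra time would enter the risk contrast itself.

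A related gap exists even with exact 5-year retests. A mixed model whose only named predictor is risk category compares score levels; it compares decline only once time and risk by time are included.

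**Working it through.** The plan gives no figure for this point that could be reproduced. The sample size of 965 has no derivation and is used below only to turn a share into a count.

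**1. Dates.** Inputs: baselines 2014-2017 (METHODS / DESIGN, Procedure); document date 6 July 2019 (title page).
- Five-year dates run from 1 January 2019 to 31 December 2022.
- Only baselines before 6 July 2014 have a 5-year date before the document date. The longest overrun on that date is 186/365.25 = 0.51 year.
- If baselines were spread evenly over the 1,461 days (assumption), the share is 186/1461 = 12.7%, and 0.127 x 965 is about 123 patients.

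**2. Intervals under different retest schedules.** The documents give no schedule, so every row is an assumption, with baselines spread evenly.

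| Schedule | Resulting interval |
|---|---|
| Each patient on own anniversary | 5.0 years for all |
| Anniversary, overdue patients seen on the document date | mean 5.03, SD 0.10, maximum 5.51 years |
| Campaign of 2 or 3 years from mid-2019, called in baseline order, none before 5 years | maximum 5.5 years |
| Campaign of 1, 2 or 3 years from mid-2019, called at random, none before 5 years | SD 0.29, 0.55, 0.83 years; 3%, 14%, 26% seen after more than 6 years |
| Campaign of 1 to 3 years from the document date, ignoring baseline date | SD 1.2 to 1.4 years, range about 1.5 to 8.5 years |

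Second row: mean excess = 0.127 x 0.51/2 = 0.03 year; SD = sqrt(0.127 x 0.51²/3 - 0.03²) = 0.10 year.

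Fourth row: for a campaign of L years, the share seen after more than 6 years is (L - 0.5)²/(8L). This gives 0.25/8 = 3%, 2.25/16 = 14% and 6.25/24 = 26%. The SDs are from simulation.

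The last row would see many patients before 5 years, which contradicts the plan's own timing. It is shown only as the outer limit.

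**3. Effect on one patient's classification.** Assume decline of 0.02 to 0.10 SD of change per year. Shift = decline per year x excess interval. The one-sided 5% cut-off rate becomes Φ(-1.645 + shift).
- Excess 0.5 year: shift 0.01 to 0.05 SD; rate 5.1% to 5.5%.
- Excess 2 years: shift 0.04 to 0.20 SD; rate 5.4% to 7.4%.

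**4. Effect on the risk contrast.** Bias = decline per year x difference in mean interval between risk categories.
- No difference in mean interval: bias 0.
- Difference of 0.5 year (assumption): 0.01 to 0.05 SD. With linear decline, this is 0.5/5 = 10% of the mean 5-year decline.

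**5. What the named model terms estimate.** With score = a + b(risk), b is the difference in mean score between risk categories over the two tests. With score = a + b(risk) + c·t + d(risk)·t, where t is years since baseline, the difference in decline over five years is 5 x d. Using actual t also handles unequal intervals, provided change is roughly linear over the observed range.

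**The case against.** A reader might infer that the plan treats the interval as fixed and so counts unequal follow-up as decline. The documents do not support that. The natural reading of the timing is each patient's own five years, and anniversary retests over 2019-2022 give 5.0 years for everyone. A four-year baseline period does not by itself produce unequal intervals. This stands.

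A reader might also take the document date as the start of retesting. Nothing says so, nothing shows that anyone was tested before July 2014, and the count of 123 rests wholly on an assumed even spread. This also stands.

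The shares of 14% and 26% beyond 6 years depend on a random calling order that the plan does not describe; calling in baseline order removes them entirely. The 10% figure is an assumed half-year delay divided by five, and no text suggests that higher-risk patients would be seen later. Neither figure can serve as an estimate of harm.

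Finally, the mixed-model sentence is not a full specification. It also leaves out the confounders promised just before it, and a model for repeated measures may well be meant to contain time. Age entered as age at each visit would carry elapsed time too, but the text does not say that. So the text does not exclude elapsed time, but it does not name it. The list of adjusters for the change cut-offs is more definite, and the interval is not in it.

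**Conclusion.** The point holds as a conditional omission. No retest window is stated, and neither the mixed models nor the regression-based cut-offs name elapsed time. If intervals vary, the cost is noise and some misclassification of reliable change; the risk contrast is biased only if the interval differs by risk category.

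The size is unknown from the documents because they give neither a retest calendar nor a rate of decline. If retests stay near 5 years it is small: with overdue patients seen promptly, the interval SD is about 0.10 year, and a half-year excess moves a 5% rate to at most 5.5% under the assumed decline rates. It grows only if fieldwork departs well from individual anniversaries. The change is worth making because it is nearly free and makes the models estimate decline over time, which is what the objective asks for.

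**What to change.** - Record the dates of both neuropsychological assessments. Table 1 lists no test dates, so their availability should be confirmed.
- In each mixed model, use actual years since baseline as the time variable, include risk category by time, and report the difference in decline per 5 years.
- Add the retest interval to age, sex and education in the regression-based change norms.
- Report the distribution of the interval by baseline risk category.
- Stating a target of baseline date plus 5 years with a window, and calling patients in order of baseline date, would keep intervals close. This is missing operational detail rather than an analysis error.

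The cost is SAP wording and one extra term in each norm equation. That term will be imprecisely estimated if intervals cluster tightly around 5 years, in which case it also matters little. If retesting is run as a campaign, interval will be tied to baseline calendar date, and the report should say so.
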